3.0 Study Endpoints/Events/Outcomes

- 3.1 Primary Endpoint/Event/Outcome:

Change in Dementia Quality of Life [Time Frame: Baseline, 3-months, and 6-months]

The 21-item modified Dementia Quality of Life instrument is a self-report survey that assesses various domains of quality of life in the person with dementia.

Change in Cantril quality of life ladder [Time Frame: Baseline, 3-months, and 6-months]

The Cantril quality of life ladder is a single item survey that asks respondents to rate their overall quality of life on a scale of 0 (bottom of the latter) to 10 (top of the ladder).

- 3.2 Secondary Endpoint(s)/Event(s)/Outcome(s):

Pleasant events and activities of person with memory concerns [Time Frame: 3-months and 6-months]

The Pleasant Events and Activities-AD Schedule Short Form is a 17-item self-report survey that measures the degree of enjoyment persons with dementia have engaging in a range of activities.

Change in the frequency and quality of social interactions of persons with memory concerns [Time Frame: Baseline, 3-months, and 6-months]

Series of weekly, self-report calendar measures on types and quality of social interactions, developed for this study.

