5.3 Follow-Up

“Data were collected at three time points: baseline, 3 months, and 6 months. Caregivers completed all surveys on behalf of the person with memory loss. Participants were asked for their opinion of their relative with memory loss (eg “How often does your relative feel confident?”). At baseline, surveys for participants caring for a person with memory loss measured ADLs, memory impairment, memory and problem behaviors, social interaction, and quality of life as well as demographic questions asking about themselves and the person with memory loss. Participants with memory loss who did not have a caregiver completed surveys on their own behalf. They received a slightly different version of the survey with questions being asked in reference to themselves (eg, “How often do you feel confident?”). Their baseline survey measured ADLs, memory impairment, social interaction, and quality of life as well as demographic questions about themselves. Surveys administered at 3 and 6 months were identical to the baseline surveys except that they did not include demographic questions. At 3 and 6 months, participants in the intervention group completed an additional feasibility and utility checklist. Participants were given the option to complete an online or paper version of the surveys.” (see <https://www.ncbi.nlm.nih.gov/pmc/articles/PMC6715400/>)

SOCIAL PROTOCOL (HRP-580)**PROTOCOL TITLE:** Social Support Aid for People with Dementia**VERSION DATE:** 5/8/2017**5.4 Individually Identifiable Health Information**

Survey data per above were relied upon.

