17.0 Statistical Considerations

17.1 Data Analysis Plan From:

<https://www.ncbi.nlm.nih.gov/pmc/articles/PMC6715400/>.

“Recruitment, Randomization, and Retention

Chi-square and t tests were used to determine if participant demographics in the intervention and control groups were significantly different ($P<.05$). Chi-square and t tests were also used to compare participants who were lost to follow-up with those who were not.

Feasibility and Utility

Participants in the intervention group were asked to complete an additional survey at 3 and 6 months to assess their perceptions of feasibility and utility. This checklist included 15 Likert scale items asking participants to rate their level of agreement with statements such as “the technology works well,” “SSA was easy to use,” and “my relative felt lost using SSA” ($\alpha=.89$).

Assessment of Intervention Effect

Descriptive statistics were calculated for measures of quality of social interaction and quality of life. Social interaction quality was measured by asking participants to rate their satisfaction with the following types of communication: visits, phone calls, mail correspondence, and computer correspondence. Quality of life was measured using the Pleasant Events Schedule-Alzheimer’s Disease (PES-AD; frequency $\alpha=.84$; enjoyment $\alpha=.76$) and Dementia Quality of Life (DQoL; $\alpha=.92$). The PES-AD asks with what frequency and level of enjoyment the person with memory loss experiences a list of pleasant activities (eg, being outside, listening to music, laughing). The DQoL asks participants to use a Likert scale to rate how often the person with memory loss feels a certain way (eg, satisfied, cheerful, angry, worried).

We imputed missing data using a Markov chain Monte Carlo method to conduct a five-fold multiple imputation. Analyses were conducted as intention to treat. Change scores were calculated to determine differences between outcomes at baseline and 6 months. To determine whether changes in satisfaction and quality of life in the intervention group were significantly different than changes in the control group, t tests were used. Statistical significance was assessed using two-tailed tests with a significance level of $P=.05$.

SOCIAL PROTOCOL (HRP-580)

PROTOCOL TITLE: Social Support Aid for People with Dementia

VERSION DATE: 5/8/2017

Qualitative Analysis

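### Section 3.1 declares two primary outcomes, but section 17.1 describes no analysis of one of them (the Cantril ladder) and does not carry over the section 3 tiers

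*Combined protocol and SAP*

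**What the plan says.** Section 3.1 lists two primary outcomes: change in DQoL and "Change in Cantril quality of life ladder [Time Frame: Baseline, 3-months, and 6-months". Section 3.2 lists two secondary outcomes. The first is PES-AD, an instrument that "measures the degree of enjoyment persons with dementia have engaging in a range of activities", with time points at 3 and 6 months. The second is "Change in the frequency and quality of social interactions of persons with memory concerns", recorded on weekly calendar measures developed for the study.

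The analysis is in section 17.1; section 17.3 only refers back to it. Section 17.1 names PES-AD (frequency and enjoyment) and DQoL as its quality-of-life measures. For social interaction, participants "rate their satisfaction with the following types of communication: visits, phone calls, mail correspondence, and computer correspondence". Change scores run from baseline to 6 months, and t tests are used "To determine whether changes in satisfaction and quality of life in the intervention group were significantly different than changes in the control group". One rule covers all of them: "Statistical significance was assessed using two-tailed tests with a significance level of" .05. The analysis is by intention to treat with five-fold multiple imputation.

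Section 5.3 does not settle whether the ladder was administered. Its list of baseline content for caregivers includes "memory and problem behaviors, social interaction, and quality of life as well as demographic questions asking about themselves" but names constructs, not instruments.

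**The concern.** A declared primary outcome should have a described analysis. Here the ladder has none, and a secondary measure stands beside DQoL under the heading of quality of life, the construct that both primaries address. A reader who has only 17.1 would not know that the ladder was a primary outcome or that PES-AD was not.

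Section 1.1 sets out to evaluate whether the aid brings benefit, so it matters which results carry that conclusion. If one primary goes unreported and a secondary is read in its place, the choice of outcome can bias the overall impression even when each test is sound. The mismatches with 3.2 add to this, because it is unclear which scores, and how many, are being compared.

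**Working it through.** The plan gives no power or overall error figure to reproduce (17.2 is marked not applicable). The main check sets the sections side by side.

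| Outcome | Section 3 | Section 17.1 |
|---|---|---|
| DQoL | Primary; baseline, 3 and 6 months | t test on change from baseline to 6 months |
| Cantril ladder | Primary; baseline, 3 and 6 months | Not mentioned |
| PES-AD | Secondary; 3 and 6 months; enjoyment | Quality-of-life measure beside DQoL; change from baseline; frequency and enjoyment |
| Social interaction | Secondary; weekly calendar; frequency and quality | Satisfaction with four types of communication |

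**Baseline PES-AD.** Section 5.3 says the follow-up surveys matched the baseline ones apart from demographics, so a baseline PES-AD may exist. The time frame in 3.2 does not include one.

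**Social interaction.** The documents do not say whether the calendar in 3.2 and the ratings in 17.1 are the same instrument. Section 17.1 describes no analysis of interaction frequency.

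**Number of tests.** Only the 6-month change is tested, so the 3-month visit adds none. I assume one DQoL total score, since domain tests are not described.
- Four ratings and two PES-AD parts tested singly: 4 + 2 + 1 = 7.
- Ratings pooled: 1 + 2 + 1 = 4.
- PES-AD also pooled: 1 + 1 + 1 = 3.

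The plan does not say which applies.

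**Error in the primary tier.** A two-sided .05 test has a chance of .05 / 2 = .025 of a false benefit.
- DQoL alone, as 17.1 stands: 2.5%.
- DQoL and Cantril, both unadjusted: at most 2 × .025 = 5%, whatever the correlation.
- If the two are independent: 1 − .975² = 4.9%. At an assumed correlation of 0.9, numerical integration of the equicorrelated normal model gives 3.5%.
- Counting either direction, under independence: 1 − .95² = 9.75%.

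**Illustration only: any tested measure counts as benefit.** The documents state no such rule. The chance of at least one false benefit is 1 − .975^k for k independent tests. For correlation ρ it is 1 − ∫ φ(x) Φ((1.96 − √ρ·x) / √(1 − ρ))^k dx.

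| k | ρ = 0 | ρ = 0.5 | ρ = 0.9 |
|---|---|---|---|
| 3 | 7.3% | 6.3% | 4.2% |
| 4 | 9.6% | 7.8% | 4.7% |
| 7 | 16.2% | 11.5% | 5.7% |

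Simulated t tests with an assumed 24 per arm agree: 7.2% for k = 3 and 16.2% for k = 7 at ρ = 0.

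**Precision.** Section 13.0 gives 48 randomized, and 5.2 gives a 1:1 ratio; arm sizes are not stated. With an assumed 24 per arm, the 95% confidence half-width is t(.975, 46) × √(1/24 + 1/24) = 0.58 SD. With 20 and 24 completers (all four losses were in the intervention arm) it is t(.975, 42) × √(1/20 + 1/24) = 0.61 SD. These are rough guides, because the planned analysis imputes missing data and that effect is not quantified here.

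**The case against.** The best defence is that section 3 already sets the tiers, and an analysis section that does not repeat them does not cancel them. Testing secondary outcomes at an unadjusted .05 is ordinary in a pilot with no power analysis. This stands, and it removes most of the multiplicity concern.

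A reader might infer from the single .05 rule that the trial's chance of a false claim is between 4% and 16%. The documents do not support that. No section says that any one significant measure establishes benefit, and the primary tier as tested stands at 2.5%. The range also needs 3 to 7 tests and correlations of 0 to 0.9, all assumed. Neither end is a bound: separate DQoL domain tests would raise the top, and the bottom depends on stopping at 0.9. Positive correlation is likely, since "Caregivers completed all surveys on behalf of the person with memory loss" where there was a caregiver.

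A reader might also infer that the ladder was measured and then dropped because of its result. That is not supported either. Section 17.1 is an extract quoted from the publication, and the documents do not show whether the ladder was collected.

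A further fair point is that a multiplicity procedure chosen after the results are known cannot give prospective error control. This stands too, and it shapes the fix.

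None of these answers the main point: a declared primary has no described analysis.

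**Conclusion.** The concern holds as an inconsistency between sections 3 and 17.1. The plan as written yields no between-group result for one of two declared primaries, does not carry the tiers into the analysis, and describes PES-AD and social interaction differently from 3.2. This follows from the text and needs no assumption.

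The error at stake within the primary tier is small: at most 5% for a false benefit on at least one of the pair if both are tested unadjusted, against 2.5% for one test. The bound does not depend on the correlation. Severity is minor, since the study is a completed pilot. Confidence is high on the missing Cantril analysis. It is lower on any wider multiplicity figure, because the number of tests and their correlation are not given.

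**What to change.** Add a dated note to 17.1, marked as written after study completion, and leave the quoted published text as it is.

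1. Add the between-group comparison of Cantril change from baseline to 6 months, using the same imputation and intention-to-treat approach, or state that the ladder was not collected.
2. Base any conclusion of benefit on the two 3.1 primaries taken together, and report both whatever they show. If significance is claimed on only one, say that two primaries were tested and that any adjustment is post hoc.
3. Report PES-AD and social interaction satisfaction as secondary and supportive. State how many scores are tested, and reconcile their definitions and time points with 3.2.
4. Give the between-group difference and 95% confidence interval for every outcome. With half-widths near 0.6 SD, a non-significant result would not exclude moderate effects, and the intervals make that visible.

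The cost is one further analysis if the ladder data exist, intervals for the comparisons already made, and a short note. No new data collection is needed.

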17.2 Power Analysis: n/a

17.3 Statistical Analysis: Please see section 17.1 above

17.4 Data Integrity: Data cleaning and review of frequencies and other univariate

procedures are used to ensure that the final analytic data sets are accurate.

18.0 Health Information and Privacy Compliance

Individually Identifiable Health Information: for guidance regarding the use, collection, storage and sharing outside of the covered entity of identifiable health information please see: [UMN Privacy Office Policies](#) and/or [Fairview Health Services Privacy Policies](#), and [UMN HIPAA Agreement Templates](#). For research conducted at Gillette Children's Specialty Healthcare refer to [Gillette Research Administration](#) for guidance.

Under the HIPAA Privacy Rule, research studies at the University are permitted to use and disclose protected health information with the authorization of the research participants, or without individual authorization in limited circumstances.

18.1 Select which of the following is applicable to your research:

My research does not require access to individual health information and therefore assert HIPAA does not apply.

I am requesting that all research participants sign a HIPCO approved HIPAA Disclosure Authorization to participate in the research (either the standalone form or the combined consent and HIPAA Authorization).

I am requesting the IRB to approve a Waiver or an alteration of research participant authorization to participate in the research.

Appropriate Use for Research: [Explain how you will ensure that only records of patients who have agreed to have their information used for research will be reviewed.](#)

SOCIAL PROTOCOL (HRP-580)

PROTOCOL TITLE: Social Support Aid for People with Dementia

VERSION DATE: 5/8/2017

An external IRB (e.g. Advarra) is reviewing and we are requesting use of the authorization language embedded in the template consent form in lieu of the U of M stand-alone HIPAA Authorization. Note: External IRB must be serving as the privacy board for this option.

18.2 Identify the source of Private Health Information you will be using for your research (Check all that apply)

I will use the Informatics Consulting Services (ICS) available through CTSI (also referred to as the University's Information Exchange (IE) or data shelter) to pull records for me

I will collect information directly from research participants.

I will use University services to access and retrieve records from the Bone Marrow Transplant (BMPT) database, also known as the HSCT (Hematopoietic Stem Cell Transplant) database.

I will pull records directly from EPIC.

I will retrieve record directly from axiUm / MiPACS

I will receive data from the Center for Medicare/Medicaid Services

I will receive a limited data set from another institution

If the limited data set used will contain information from somewhere other than the University of Minnesota or MHealth, then you must enter into a Data Use Agreement with the data source. You may use the University's standard Data Use Agreement or another form approved by the health information Privacy & Compliance Office. Please upload in ETHOS the Data Use Agreement you will use for this transfer of information.

If you do not have a Data Use Agreement in place, you may submit your protocol for review however, you must complete a Data Use Agreement before you can receive the Limited Data Set. If you have questions about Limited Data Sets, please refer to <http://www.healthprivacy.umn.edu/policies-procedures/creating-limited-data-set>, or contact the privacy office at [contact], or by e-mail at [contact].

Other. Describe: **Describe in detail the source of the information.**

18.3 Explain how you will ensure that only records of patients who have agreed to have their information used for research will be reviewed.

All information was collected from surveys and interviews directly with participants who consented. See above for more information about how data were managed and secured.

SOCIAL PROTOCOL (HRP-580)

PROTOCOL TITLE: Social Support Aid for People with Dementia

VERSION DATE: 5/8/2017

18.4 Approximate number of records required for review:

Please see above

18.5 Please describe how you will communicate with research participants during the course of this research. Check all applicable boxes

This research involves record review only. There will be no communication with research participants.

Communication with research participants will take place in the course of treatment, through MyChart, or other similar forms of communication used with patients receiving treatment.

Communication with research participants will take place outside of treatment settings. If this box is selected, please describe the type of communication and how it will be received by participants.

Communication took place in-person, over the phone, and via email.

Please see above. Older completed studies, following study de-identification, are also stored in Mayo storage where appropriate

18.12 Disposal of Documents:

We do not plan to dispose documents.

19.0 Confidentiality

19.1 Data Security: Please see above for our steps to ensure confidentiality of all data as well as its security. The consent form is not located within any medical or similar record of participants.

20.0 Provisions to Monitor the Data to Ensure the Safety of Participants

20.1 Data Integrity Monitoring.

See below

20.2 Data Safety Monitoring. As the proposed project will pose minimal risks to study participants the Principal Investigator (PI), [name], will serve as the primary monitoring entity of this study. As noted above, the proposed study involves no invasive procedures and there will be no physical risks to study participants. The consideration of need is potentially stressful, and thus there are possible psychological risks for the caregiver a relative with Alzheimer's disease and related dementia (ADRD). The potential social or legal risks for the participants relate only to possible violations of confidentiality.

Ongoing review of protocol and human subjects research compliance occurred during regular project meetings and [name]. During these meetings [name] worked with project staff to minimize research-associated risk and protect confidentiality of participant data. Research staff were trained to interview in ways that were non-threatening, friendly, and respectful. We emphasized to all participants that they did not have to complete any question they did not want to answer, and that the interview could be terminated at any time according to their wishes. We stressed to participants that their decision to discontinue the study would in no way affect the services they are receiving from the University of Minnesota or other entities.

In the event a participant became upset during the interview process (which did not occur), research staff would contact [name], who will be available for consultation. If a participant was in crisis because of their care situation or some other reason, research staff were be instructed to consult with [name] (which again did not occur). With the participant's permission, we would contact the appropriate resource person in an external agency (e.g., the Alzheimer's Association). If a member of the research team identified neglect or other

SOCIAL PROTOCOL (HRP-580)

PROTOCOL TITLE: Social Support Aid for People with Dementia

VERSION DATE: 5/8/2017

potentially inappropriate care practices (which did not occur), the state Ombudsman will be notified to protect the rights of persons with dementia and their families.

All information obtained from participants was strictly confidential and will not be released except at the express written request of the study participant. All electronic data are maintained on [name] office computer and the HST secure project folder.

21.0 Compensation for Research-Related Injury

21.1 Compensation for Research-Related Injury: Not applicable

21.2 Contract Language: Not applicable

22.0 Consent Process

Note: The process and documentation plan must follow "[SOP: Informed Consent Process for Research \(HRP-090\)](#)" and "[SOP: Written Documentation of Consent \(HRP-091\)](#)."

22.1 Consent Process (when consent will be obtained): Please see above.

22.2 Waiver or Alteration of Consent Process (when consent will not be obtained, required information will not be disclosed, or the research involves deception): Not applicable.

22.3 Waiver of Written/Signed Documentation of Consent (when written/signed consent will not be obtained): Not applicable.

22.4 Non-English Speaking Participants: Not applicable.

22.5 Participants Who Are Not Yet Adults (infants, children, teenagers under 18 years of age): Not applicable.

22.6 Cognitively Impaired Adults, or adults with fluctuating or diminished capacity to consent: Please see above.

22.7 Adults Unable to Consent: Please see above.

23.0 Setting

23.1 Research Sites: Please see above.

23.2 International Research: Not applicable.

23.3 Community Based Participatory Research: Not applicable.

24.0 Multi-Site Research

Not applicable.

25.0 Coordinating Center Research: Not applicable

26.0 Resources Available

SOCIAL PROTOCOL (HRP-580)

PROTOCOL TITLE: Social Support Aid for People with Dementia

VERSION DATE: 5/8/2017

26.1 Resources Available: Please see above for details on funding and other resources available to conduct this study, which is now complete.

